### 5.3 Safety Outcomes

The questionnaires used for the secondary outcome will also contain questions to measure the safety of the devices. These questions will specifically address unexpected noise or behaviour from the devices. Unexpected behaviour includes unprovoked feedback or whistling, distorted sounds or artefacts, spontaneous muting or the shutting off of the device, and any unexplained warning signals, beeps, or loud sounds.

## 6. STUDY DESIGN

This is a controlled, single blinded, comparative clinical evaluation conducted monocentric at the premises of Bernafon AG in Bern, Switzerland.

The exploratory study is based on a population of 18-20 hearing impaired people that have a hearing loss appropriate for the IMD.

As the comparator, the subjects will be fit with an SP in the same hearing aid as the IP. Additionally, a control situation will be the P1 or general program that is intended for all daily listening situations excluding music giving the subjects 3 programs within the IMD.

There is no placebo or device that does not provide amplification. The study consists of two field and three lab tests. A randomized and single-blinded, single-arm design will be used for the field tests. The lab test order will be randomized and single-blinded.

The study will consist of hearing-impaired subjects with hearing loss ranging from mild to profound and appropriate for testing of the IMD. The lab testing (AMP) will be single blinded and randomised and performed in a simulated environment. The blinding and randomization refer to the position that the SP and IP have within the programming. When multiple programs are fitted to the hearing aid the subject switches programs with a button that scrolls through the programs. The subjects will not know if the SP or the IP are in second or third position during both the field and the lab testing.

The subjects are expected to participate for approximately 1 month. The testing will include a combination of a field and lab tests. There are three lab tests during which the participants will not spend more than 2 hours in the clinic (including breaks). The field test periods will not last more than 10 +/- 7 days.

The sequence for the testing will begin with the screening appointment in which participants are invited to the clinic to determine if they are candidates for the trial. The entire test procedure will be

explained, and they will be given a Patient Information and Informed Consent which will need to be signed, dated, and returned before any testing begins. If they choose to participate, a hearing test will be made to determine if they have an appropriate hearing loss. They will be fitted with the IMD with a general program (P1) as all test subjects will first wear hearing aids for an initial field period of 10 +/- 7 days to become accustomed to the devices. They will perform the first lab test in the unaided and aided (P1) conditions. They will be randomized regarding the program placement (P2 or P3) for the IP and SP.

The following appointments will include the fitting of the SP and the IP (as either program 2 or 3, according to the randomization) and the lab tests in the clinic performed in the aided condition with P2 and P3. There will be a total of 3 appointments. There is an appointment before and after each field test. Each appointment will not exceed 2 hours. During the lab tests in the clinic they will participate in the AMP test. Test subjects will be given questionnaires to complete at home and in the clinic.

After they have completed all appointments, they will be notified that the trial is over. They will be reminded that they are welcome to come to the clinic for any maintenance or other follow-up of their own hearing aids.

## **6.1 Methods of minimising bias**

### **6.1.1 Randomization**

A randomized assignment of the position of SP and IP will be used for the field trial period that includes P2 and P3 and consequently the lab tests. The position of the SP and the IP (as either program 2 or 3) will be based on a list created by the statistician. This reduces bias by using a different scroll position as the earlier position has a better chance of scoring higher due to the more prominent placement and likelihood that subjects might not always scroll to the 3rd program. The randomization list will not be concealed from the PI but should be in the ISF so that the PI knows in which condition order to test each subject.

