### **7.3 Assignment to study groups**

For the field tests the allocation is a randomized single-arm design, meaning that all participants will receive the test program (IP) and the comparator (SP). Half of the test subjects will have the SP assigned to the second program position and half to the third with a possible maximum imbalance of 2.

For the adaptive music perception test in the lab, the assignment to the test condition order will follow the randomization of the field test. The subjects will perform the lab test with P2 at visit 2 and P3 at visit 3. Because the assignment to P2 and P3 is randomized it will automatically randomize the test condition order. This will minimize bias created when one test condition is tested in the final or last position all the time.

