### **7.4 Criteria for withdrawal / discontinuation of participants**

Participants are allowed to withdraw from the study at any time and for any reason. They do not have to share the reasons with the investigator. They will be asked to return the IMD. If the decision to withdraw is made by the investigator, the PI will inform the subject in person that they are no longer needed for the study. Reasons for withdrawing a participant from the study could be for non-compliance during testing, unreliable responses, medical reasons such as an ear infection, or the study may need to be stopped or postponed. Any data gathered from these subjects will be used for the current study. All data will remain encoded because results are only recorded using the identification code of the subject. There are normally at least five “back-up” test participants on the list to replace those that withdraw or are withdrawn. The “back-up” participants will have already been screened and deemed to be appropriate for the study.

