#### **11.4.2 Primary Analysis**

The study will assess the performance of the IP in comparison to the SP using a preference questionnaire. After wearing the devices for at least 10 +/- 7 days and using them in daily life and various music situations, the subjects will be asked to complete a preference questionnaire and choose between the two music programs (SP and IP).

The preference score is rated on a 5-points Likert scale: SP much better, SP better, no difference, IP better, IP much better. The score distribution is described by the minimum, median, and maximum values and tested with a Wilcoxon signed-rank test with the assumption that ordinal scores from a Likert scale reflect the within subject difference. The null hypothesis is that there is no difference between the tested protocols and the alternative hypothesis is that there is a preference for a protocol. A two-sided test will be made as the IP has not been tested before.

Certainty and motivation of preference will be summarized and described separately. The results of this test will be used to answer the 1st and 2nd research questions.

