3.2 Randomization

The study is based on repeated measures with the SP and the IP. Participants are asked to switch between the listening programs in a given condition (practice, rehearsal, or concert) in order for them to gather comparable experiences while playing and listening to music.

Program allocation effect, i.e. higher likelihood to use program 2 than 3, will be compensated by randomizing the order of the tested protocols in the listening program slot. This risk is outbalanced by the benefit of directly comparing the same listening situation with both programs.

The program order will be randomized, and the lab test order will follow the program order randomization. The active participation of the investigator is required for the IP resulting in a single blind (participant only) design. The randomization list will be provided to the investigator by the statistician and documented before the recruitment process starts.

The randomization list will be generated with a random permuted block method and a random digit link to control any potential order inequality. Pocock (1983, p 77) provides a link between random digits and the structure of blocks for four patients and 2 treatments (order). No stratification is foreseen because no confounding factors have been identified at this stage of the study design.

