4. STATISTICAL PRINCIPLES

4.1 Levels of confidence intervals and p-values

Inferential statistical tests will be performed using the two-sided $\alpha = 0.05$. All reported p-values greater than or equal to 0.001 will be rounded to three decimal places and p-values less than 0.001 will be displayed as " <0.001 ". Confidence intervals are computed from observed data at 95%.

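### The primary signed-rank test ignores program slot, although the trial randomises slot because it expects slot to affect the rating

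*Protocol*

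**What the plan says.** Protocol 6.1.1 explains why slot is randomised: "the earlier position has a better chance of scoring higher due to the more prominent placement", and participants may not always scroll on to the third program. SAP 3.2 treats the matter as settled by design: the effect "will be compensated by randomizing the order of the tested protocols in the listening program slot". The same section then foresees no stratification, on the ground that no confounders have been identified.

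Protocol 7.3 assigns half the participants to each slot order, "with a possible maximum imbalance of 2". SAP 3.2 uses permuted blocks of four. Protocol 7.4 keeps at least five screened back-ups "to replace those that withdraw or are withdrawn", and Protocol 11.5 analyses complete cases only.

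Each participant gives one primary score: "The preference score is rated on a 5-points Likert scale: SP much better, SP better, no difference, IP better, IP much better". Protocol 11.4.2 and SAP 6.2.1 both have it "tested with a Wilcoxon signed-rank test with the assumption that ordinal scores from a Likert scale reflect the within subject difference". Neither names slot as a model term, a stratum or a sensitivity analysis. The secondary models do not list it either.

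**The concern.** Randomising a nuisance factor protects against systematic bias. It does not take the factor out of the data. If slot 2 is favoured, scores shift towards IP where IP is in slot 2 and towards the default program (SP) where IP is in slot 3. A one-sample test about zero sees only the pooled distribution, so it reads this known and recorded shift as random variation.

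Two things follow. Power falls in a primary test that has only 18 to 20 participants. And if the analysed slot groups are unequal, part of the slot effect is reported as preference for or against IP, depending on which group happens to be larger.

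**Working it through.** **Figure that can be reproduced.** The documents give no effect size, SD, power or slot effect, so the sample size cannot be reproduced. The maximum imbalance of 2 can. With blocks of four, n = 20 is five full blocks, giving 10:10. With n = 18, two places of the fifth block are used. Of its 6 arrangements, 4 give 9:9 and 2 give 10:8, so 10:8 occurs one time in three.

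**Analytic model.** Score = τ + π·s + error, with s = +1 if IP is in slot 2 and −1 if it is in slot 3. τ is the IP effect, and π is half the difference between the slot groups.

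- Unadjusted variance with equal slots is multiplied by 1 + π²/SD². For a design with 80% power, (1.96 + 0.84) is divided by √(1 + π²/SD²). At π = 0.5 SD this is 2.80/√1.25 = 2.51, and Φ(2.51 − 1.96) = 0.71. At π = 0.25 and 1.0 SD the power is 0.776 and 0.508. The equivalent sample-size multipliers are 1.06, 1.25 and 2 for π = 0.25, 0.5 and 1.0 SD.
- Bias of the unadjusted mean is π(n₁ − n₂)/n, where n₁ is the group with IP in slot 2. It is 0 with equal slots, 2/18 = 0.111π at 10:8 and 4/18 = 0.222π at 11:7.

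**Simulation (assumed).** The latent variable is normal with SD 1, cut at ±0.4 and ±1.2 into five categories. The IP shift is 0.7, slot shifts of 0 to 0.9 are in latent SD, and there are 8,000 runs per scenario at two-sided 5%. The slot-adjusted test recodes each answer as slot 2 over slot 3 and compares the two slot groups by rank-sum. With no IP preference the recoded scores have the same distribution in both groups, whatever the slot effect.

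| Slot shift (±) | 0 | 0.3 | 0.6 | 0.9 |
|---|---|---|---|---|
| 10:10, signed-rank power | 79.5% | 76.7% | 66.8% | 53.8% |
| 10:10, slot-adjusted power | 78.4% | 78.2% | 76.3% | 76.9% |
| 9:9, signed-rank power | 74.9% | 71.2% | 61.7% | 45.9% |
| 9:9, slot-adjusted power | 74.1% | 72.6% | 71.0% | 69.7% |
| 10:10, signed-rank rejection, no IP effect | 4.4% | 3.9% | 2.1% | 0.9% |

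The slot-adjusted test rejects 4.3% to 4.7% of the time when there is no IP effect.

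Other cut-points (±0.5 and ±1.5) show the same pattern. At 9:9, signed-rank against slot-adjusted power is 73% vs 72% at π = 0, 65% vs 72% at π = 0.5 and 43% vs 72% at π = 1.0.

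**Unequal slots.** In the ±0.4/±1.2 model with no IP effect, a slot shift of 0.3, 0.6 or 0.9 moves a group's expected score by 0.335, 0.659 or 0.959 points. Multiplying by 2/18 gives a biased mean of 0.037, 0.073 or 0.107 points at 10:8. At slot shift 0.6, signed-rank power is about 71% at 10:8 but 52% to 54% at 8:10. The slot-adjusted test gives 72% to 73% at both.

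**Effect of losses.** If 4 of 20 participants (10:10) are lost at random, the analysed split differs by 2 with probability 0.50 and by 4 with probability 0.09.

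**The case against.** The planned test is valid. It does not inflate type I error in any scenario examined, and it becomes conservative when the slot effect is large. With 20 completers at 10:10 the bias is zero, and over the randomisation it averages to zero. At 10:8 it is at most about a tenth of a point on a five-category scale. No dropout rate is stated, and back-ups could restore balance as easily as upset it.

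The large power losses need large slot effects. A shift of ±0.6 means that the slot groups differ by 1.2 SD, against an IP effect of 0.7. The group with IP in slot 3 would then have a mean score of only 0.11. At ±0.9 that mean is −0.22, so slot would outweigh the program. At ±0.3 the loss with equal slots is 1 to 2 points. The protocol also acts on the mechanism: participants are told to use both programs equally (8.2.1), are reminded by email, and have use per program logged (8.4). The trial is exploratory, with no power target.

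All of this stands, and it limits the size of the problem. It does not explain why a factor that the sponsor expects to matter, randomises and records should be left out of the primary analysis, when including it costs almost nothing.

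**Conclusion.** The concern holds. The plan names a slot effect, randomises because of it, and then uses a primary test that cannot see it. The consequence is lost power and, when slots are unequal, a shifted estimate. It is not an excess of false positives.

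With equal slots, adjustment gains about 1 to 2 points of power at a slot shift of 0.3 SD, about 9 to 10 points at 0.6 and about 23 to 24 points at 0.9. These figures rest on the assumed latent-normal model, an IP shift of 0.7 and assumed slot effects. That the gap exists is certain; how much it costs is not. The change should be made, although the planned analysis is not invalid without it.

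**What to change.** In Protocol 11.4.2 and SAP 6.2.1:

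- Recode each answer as preference for slot 2 over slot 3, and compare participants with IP in slot 2 and in slot 3 by a two-sided Wilcoxon rank-sum test. Use exact (permutation) p-values, because five categories produce many ties. This borrows the order-adjusted comparison of a crossover, although here both programs are available at once.
- The rank-sum test does not itself give the effect, so define the estimate separately: the simple average of the two slot-group mean IP-versus-SP scores, with a 95% confidence interval. Report preference by slot beside it.
- Keep the unadjusted signed-rank test as a sensitivity analysis.
- State which list position a replacement participant takes.

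No new data are needed, since the CRF (Protocol 12.1.1) already records the program 2 assignment. If slot has no effect, the price is about 1 to 2 points of power. At 10:8 with a slot shift of 0.3, the unadjusted test rejects slightly more often (75.8% vs 73.1%), but that surplus comes from the bias. The choice should be fixed before slot results are seen.

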### **6.1.2 Blinding procedures**

The field and lab tests will be blinded as the subjects will not know in which place the SP and IP are programmed. The statistician will create a permuted block list to randomize the placement of the two music programs. The PI will follow this list.

### **6.1.3 Other methods of minimising bias**

The IMD will be programmed with a P1 to be used in general listening situations. All test subjects will wear the hearing aids for the first field test of 10 +/- 7 days with this program to become accustomed to the amplification. They will continue to use P1 during the second field test with the SP and IP added as the second and third programs. P1 will serve as a control in the circumstance that the subject's rate both the music programs poorly, to determine whether only the music programs are the problem or whether they have not accepted the device overall.

## **6.2 Unblinding Procedures (Code break)**

The blinding for the field and lab tests will be based on a permuted block list created by the statistician. The subjects will not know which program they have in the second and third positions, only that they are music programs. The list will be in the ISF so that the PI has access and knows which assignment to use for each appointment.

The study will take place in the clinic at Bernafon AG in Bern. No other sites will be used for the testing. A plan of action due to low enrolment will be to widen the number of orchestras or musical groups to which information about the trial is distributed. The initial plan is to distribute information to groups

located within a 20 km radius to avoid that participants must travel far.

## 7. STUDY POPULATION

### 7.1 Eligibility criteria

Participants fulfilling all of the following inclusion criteria are eligible for the study:

- All classifications of hearing loss (sensorineural, conductive, mixed)
- If the hearing loss is conductive or mixed, it must be approved for amplification by a physician
- All shapes of hearing loss (flat, sloping, reverse slope, notch)
- Hearing loss severity ranging from mild to profound
- German or French speaking
- Play a musical instrument
- Both genders
- Ages 18 and older
- Ability and willingness to sign the consent form

The presence of any one of the following exclusion criteria will lead to exclusion of the participant:

- Normal hearing
- Contraindications for amplification
- Active ear disease
- Don't play an instrument
- Inability to follow the procedures of the study due to language problems, psychological disorders, dementia, or other cognitive problems
- A reduced mobility making them unable to attend weekly study appointments
- A reduced ability to describe auditory impressions and the usage of the hearing aids
- Uncooperative so that it is not possible to record a valid pure tone audiogram
- A strongly reduced dexterity
- Central hearing disorders
- Bernafon employees
- Family members of Bernafon employees

### 7.2 Recruitment and screening

Bernafon has its own directory of test subjects that use the Bernafon clinic for updated fittings and general maintenance of their hearing aids. These test subjects do not consist of employees of Bernafon or family members of employees. The test subjects for the current study will first be chosen from the internal subject directory. Once the appropriate options from the internal list have been exhausted, a flyer with information about the trial will be shared with musical groups/orchestras within a 20 km radius of the city of Bern. The flyer will provide the email address of the PI of the study for further information. Additionally, participants may be recruited by word of mouth. If a current person from the directory or someone that is enrolled for the current study knows of another person with hearing loss, they may give them the contact information of the PI. The prospective person can then contact the PI if they wish to have more information and/or to make a screening appointment to determine if they're eligible to participate in the study. The PI will respond by email or phone (whichever is the preference of the possible test subject). The PI of the study is well informed and qualified to answer all questions and give information about the study. If there are any medical indications suspected during the screening, the subject will be recommended to see a physician and then return if there are no contraindications for hearing aids. During the screening discussion it will be determined whether the person

is cognitively able to act on their own behalf. Additionally, if the person comes alone or if they are accompanied will help to determine their level of independence. It will be explained to the subjects that the general compensation for their time is by means of a box of batteries and cleaning accessories.

### **7.3 Assignment to study groups**

For the field tests the allocation is a randomized single-arm design, meaning that all participants will receive the test program (IP) and the comparator (SP). Half of the test subjects will have the SP assigned to the second program position and half to the third with a possible maximum imbalance of 2.

For the adaptive music perception test in the lab, the assignment to the test condition order will follow the randomization of the field test. The subjects will perform the lab test with P2 at visit 2 and P3 at visit 3. Because the assignment to P2 and P3 is randomized it will automatically randomize the test condition order. This will minimize bias created when one test condition is tested in the final or last position all the time.

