### 5.2 Secondary Outcomes

Secondary outcomes will be measured with an adaptive music perception test (AMP) developed by Kirchberger and Russo (2015). The test uses recordings and asks the subjects to judge different aspects of music such as meter and timbre. The overall sound quality and benefit of the hearing aids in daily life will be measured with product questionnaires. The product questionnaire for the general P1 will be used to control for a general acceptance of the hearing aids and will be answered one time after the first field period. The music perception questionnaire will be used to judge sound quality of music and will be answered three times, one for each hearing aid program. The music questionnaire will be answered for P1 at the end of the first field test and for P2 and P3 at the end of the second field test.

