### **9.3 Procedures at each visit**

#### **9.3.1 Screening/First visit**

Screening visit, Day 0: The potential participants will be given the Patient Information and Informed Consent form. The trial will be explained including how many visits are expected as well as the type of testing that they will complete. They are given time during the appointment to read the information and decide whether to participate in the study. If they choose to not take part in the study, they will not sign the consent form, and the appointment will finish. If they choose to join the trial, they will sign and date the consent form. No trial activities will be performed before the consent form is signed and dated by the subject and the investigator. Subjects will receive a copy of the signed consent form. A hearing history is then taken, and otoscopy is performed. A hearing test is performed, and inclusion/exclusion criteria will be determined. The subject is then randomized regarding the assignment of the music programs (IP or SP) to program slots 2 or 3. They are fitted with the IMD based on a first fit in the software and adjusted using REM data to match the gain targets. The hearing aids will be fit only with a general program in the P1 slot. They will perform the lab test with the AMP in two conditions: unaided and aided with the general program. They are given an IFU for the hearing device. They are given a product questionnaire and a music perception questionnaire and instructed to complete them at home a day before their next appointment. Any AEs are reported in the CRF. They are scheduled for the second visit.

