#### **9.3.2 Fitting/Second visit**

Fitting Visit, Day 10 +/- 7: Otoscopy is performed, and the subjects return the completed questionnaires. The IMDs are fitted with IP and SP as specified by the randomization carried out at the first visit. The IP is optimized and fine-tuned based on comments that the subject makes about the sound while they play their instrument in the clinic. The SP is programmed without any adjustment based on the default music program offered in the software. They are instructed to switch between programs two and three when playing and listening to music for the next 10 +/- 7 days. They perform the lab test with the AMP in one condition: aided with P2. The subjects are given the music perception questionnaires and instructed to complete them at home a day before their next appointment. One questionnaire pertains to P2 and the other to P3. Any AEs are reported in the CRF. They are scheduled for the third visit.

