#### **9.3.3 Lab/Third visit**

Final Visit, Day 20 +/- 7: Otoscopy is performed. The subjects return the completed product questionnaires. They perform the lab test with the AMP in one condition: aided with P3. They complete a preference questionnaire during the appointment. They are notified that the trial has ended and those that normally wear hearing aids can return to using their own devices. They will return the IMD to the clinic. Any AEs are reported in the CRF. Those that are on the Bernafon subject list and normally wear devices fitted by the Bernafon clinic are reminded to return to the clinic for normal maintenance of their hearing aids. Anyone that would like to join the Bernafon clinic are also welcome to do so.

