6.2.2 Adaptive Music Perception (AMP) Test

The AMP test is based on an adaptive procedure that provides the threshold reflecting the amount (time, loudness, pitch...) that each participant can detect above chance. The thresholds are measured on ratio scales: duration in milliseconds, pitch in hertz, loudness in decibels. Kirchberger & Russo (2015) indicate that the thresholds might be influenced by different covariates, like degree of hearing loss or music experience, and by the type of signal processing. Measured thresholds will therefore be modelled by a linear mixed-effect regression with backwards selection based on the variation inflation factor (VIF). This gives a complex picture for the coefficient interpretation as there are 4 test conditions: unaided, aided general program, aided SP, and aided IP. Planned contrasts will be considered:

1. Unaided vs Aided

2. General vs Music-specific programs
3. IP vs SP

The 3rd research question will be answered with a paired t-test on each subscale comparing threshold from the IP to the thresholds from the SP.

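### The AMP comparison of IP with SP ignores the visit at which each program was tested, and the General vs Music contrast cannot be separated from visit

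*Protocol*

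**What the plan says.** Four AMP conditions are spread over three visits. Protocol 7.3 gives the rule for the two music programs: "The subjects will perform the lab test with P2 at visit 2 and P3 at visit 3". By visit:

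- Visit 1 (Protocol 9.3.1): "They will perform the lab test with the AMP in two conditions: unaided and aided with the general program".
- Visit 2 (Protocol 9.3.2), when IP and SP are first programmed: "They perform the lab test with the AMP in one condition: aided with P2".
- Visit 3 (Protocol 9.3.3), after the second field period: "They perform the lab test with the AMP in one condition: aided with P3".

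Which of IP and SP sits in P2 is randomised in permuted blocks of four (SAP 3.2). Protocol 7.3 relies on this to deal with test-order bias and allows a maximum imbalance of 2.

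For the analysis, SAP 6.2.2 states: "The 3rd research question will be answered with a paired t-test on each subscale". Protocol 11.4.3 says the same. Both also plan a "linear mixed-effect regression with backwards selection based on the variation inflation factor (VIF") with three contrasts: Unaided vs Aided, General vs Music-specific, and IP vs SP. Degree of hearing loss, music experience and signal processing are mentioned as possible influences. Neither document puts a visit, slot, period or sequence term into the AMP analysis.

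The music questionnaire has a related layout. Protocol 5.2 says: "The music questionnaire will be answered for P1 at the end of the first field test". The P2 and P3 forms are completed at the end of the second field test.

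**The concern.** The order of testing is randomised, but the analysis does not use that order. Each within-person IP minus SP difference contains the visit 2-to-3 shift, with a plus or minus sign set by slot. The sponsor has reason to expect some shift: Protocol 7.3 is concerned about a condition always being tested last, Protocol 6.1.3 allows time to become accustomed to amplification, and Protocol 10.1.1 lists habituation as likely. A paired t-test treats the alternating sign as noise. With 18-20 participants and no effect size behind that number, this gives up precision on the AMP answer to research question 3.

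The second issue is one of interpretation. The general program is AMP-tested only at visit 1 and the music programs only at visits 2 and 3. A General vs Music difference could therefore be practice or acclimatisation alone.

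**Working it through.** **Inputs.** From the documents: the visit schedule (Protocol 7.3, 9.3.1-9.3.3), n = 18-20 (SAP 3.3), two-sided alpha 0.05 (SAP 4.1), blocks of four (SAP 3.2). Not in the documents, so assumed: the visit 3 minus visit 2 shift π, taken from 0 to 1 σ, where σ is the SD of the paired difference without the shift; and the true IP-SP effect τ, set to give the paired t-test 80% power at π = 0 (0.70 σ at n = 18, 0.66 σ at n = 20).

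**1. The plan's own figure.** Enumerating the six permuted blocks of four gives a maximum imbalance of 2 at any stopping point, as Protocol 7.3 states. With full blocks as randomised, n = 20 ends 10:10. At n = 18 the last two places come from a part-used block. Two of the six blocks begin with the same order twice, so a 10:8 split has probability 2/6 = 1/3.

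**2. Model for IP vs SP.** Participant difference: D = τ + π + e if IP is in P3, and D = τ − π + e if IP is in P2.

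- Planned test: t = mean(D) / (s/√n), n − 1 df. The expected s² is σ² + π² · 4n₁n₂/[n(n − 1)]. At 9:9 the multiplier is 4·81/(18·17) = 1.059.
- Two-period crossover: estimate = (mean D in slot group 1 + mean D in slot group 2)/2, pooled within-group SD, n − 2 df. π cancels.

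Rough check at π = 0.5 σ: √(1 + 0.25·1.059) = 1.125, times the ratio of t quantiles 2.110/2.120, gives about 1.12. The simulation gives the same.

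**3. Simulation, 9:9 (n = 18).**

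| π/σ | Power, paired t | Power, adjusted | Size, paired t | Interval width, paired t / adjusted |
|---|---|---|---|---|
| 0 | 80% | 80% | 5.0% | 1.00 |
| 0.25 | 78% | 80% | 4.4% | 1.03 |
| 0.5 | 72% | 80% | 2.9% | 1.12 |
| 1 | 49% | 80% | 0.6% | 1.43 |

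Adjusted size is 5% throughout. At 10:10 (n = 20) the results agree to within about a percentage point.

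**4. Bias when the split is uneven.** The unadjusted mean is off by π(n₁ − n₂)/n. At 10:8 this is 2π/18 = 0.11π, that is 0.03, 0.06 and 0.11 σ at π = 0.25, 0.5 and 1 σ. Its direction between IP and SP is not known in advance. The adjusted estimate has no such bias.

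**5. Cost of adjusting when π = 0.** About 0.3 points of power at 9:9 and under 1 point at 10:8.

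**6. What can be estimated.** With 18 subject effects, 3 condition effects and 2 visit effects there are 18 + 3 + 2 = 23 columns, and the rank is 22. IP vs SP and unaided vs P1 are estimable. General vs Music and unaided vs the mean of all aided runs are not. Without a visit term, and with a the visit 1-to-2 shift, General vs Music carries a + π/2, and pooled Unaided vs Aided carries (0 + a + a + π)/3 = 2a/3 + π/3.

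**7. Visit and VIF selection.** A three-level visit factor is exactly collinear with condition, so selection on VIF would remove part of it. A single visit-3 indicator has R² = 1/3 against condition, hence VIF = 1/(1 − 1/3) = 1.5.

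**The case against.** The plan has already dealt with the main risk: randomising slot order keeps IP vs SP free of systematic bias. What is lost is precision on one secondary outcome of a trial the SAP calls a pilot, with no power target for AMP. The 80% benchmark and the range for π are assumptions. By visit 2 participants have done the AMP test twice and worn the device for a field period, so the later shift may be small; at 0.25 σ the loss is about 2 points. IP vs SP is also a contrast in the mixed model, whose covariate list is open. A visit-3 indicator with VIF 1.5 would probably survive selection. General vs Music and Unaided vs Aided answer no stated research question, and the SAP treats P1 data as a reference.

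Most of this stands, and it limits the weight of the point. It does not remove it. The music programs themselves are new at visit 2, so earlier practice does not show that π is zero. SAP 6.2.2 gives the AMP part of research question 3 to the t-test, and an open covariate list does not specify a visit term. Both aliased comparisons are listed as planned contrasts with no caveat.

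Two qualifications apply. Zero bias at n = 20 holds for full blocks as randomised; withdrawals and complete-case exclusion could leave 11:9 and a bias of 2π/20 = 0.10π. The absence of extra false positives is a two-sided statement: at 10:8 and π = 0.25 σ the favoured tail is about 2.9% against 2.5%, which is negligible.

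**Conclusion.** The point holds, with modest weight. The paired t-test for AMP IP vs SP is valid but conservative, and discards precision that the randomised slot order makes available. The loss ranges from nothing at π = 0 to a 43% wider interval and 49% instead of 80% power at π = 1 σ; that range is assumed, since the documents give neither the shift nor the SD. General vs Music is not identifiable as a program effect in either the AMP or the questionnaire data, whatever the size of the shift. Unaided vs Aided is affected only if the visit 2 and visit 3 runs are pooled into it. The timing of the AMP visits does not affect the primary preference analysis. Nor does the problem extend to the questionnaire comparison of IP with SP, because those two forms cover the same field period and are returned together at visit 3.

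**What to change.** Amend SAP 6.2.2 and 6.2.3, and Protocol 11.4.3 to match:

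1. For IP vs SP on each AMP subscale, replace the paired t-test with the two-period crossover estimate: the average of the two slot-group mean differences, pooled within-group SD, n − 2 df. Equivalently, fit a mixed model to the SP and IP runs with visit as a fixed effect exempt from backward selection. Slot and visit coincide for AMP, so one term covers both. If the four-condition model is kept, use a single visit-3 indicator.
2. Report General vs Music, for AMP and for the questionnaire, as descriptive, with a statement that it cannot be attributed to the music programs.
3. Restrict Unaided vs Aided to unaided vs P1, both measured at visit 1.

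The cost is SAP and protocol wording and one degree of freedom (under 1 point of power if there is no shift). Visits, forms and participant burden do not change. One limit remains: the adjusted estimate averages over just-fitted and after-use testing, and cannot show whether the IP-SP difference itself changes with experience.
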